### 5.5.3.2 *Intra-Off-Site Reader Variability*

Intra-reading variability will be analyzed in a subgroup of 10% of subjects randomly selected for whom the off-site readers have re-read the images.

Intra-central reader variability will be studied by a Bland-Altman graph [3]:

- Average of 1st and 2nd reading on X axis.
- Difference 2nd reading - 1st reading on Y axis.
- Horizontal lines at 0, Mean + 1.96SD and Mean - 1.96SD, where Mean and SD are the mean and the SD of the averages of 1st and 2nd readings.

One scatter plot per reader will be presented with different colors for each dose of P03277.

Descriptive statistics and the Intra-Class Correlation (ICC) [4] will also be provided. It will be based on a one-way random effect model without observed effect:

$$Y_{ijk} = \mu + \alpha_i + \varepsilon_{ijk}$$

with  $\alpha_i \sim N(0, \sigma_{\alpha}^2)$  and  $\varepsilon_{ijk} \sim N(0, \sigma_{\varepsilon}^2)$  and  $\varepsilon_{ijk}$  is independent of  $\alpha_i$ .

$$\text{JCC} \equiv \sigma_a^2 / (\sigma_a^2 + \sigma_c^2)$$

which is estimated by

which is estimated by

$$(MS_{\alpha} - MS_c) / (MS_{\alpha} + MS_c)$$

where  $MS_{\alpha}$  and  $MS_{\varepsilon}$  are the mean sums of squares from the one-way ANalysis Of VAriance (ANOVA) model for between and within subjects, respectively.

CONFIDENTIAL	FORM	
	STATISTICAL ANALYSIS PLAN N° GDX-44-004	
	VERSION 1.0      DATED: 09JAN2018	Page 34 / 60

SAS® procedure used for the analyses of this secondary efficacy criterion will be the following for each off-site reader:

```

ods output OverallANOVA =icc0;
proc glm data=intra;
  class patno reading;
  model BV = patno reading;
run;
data ICC;
  retain sb sw;
  set icc0 end=last;
  if source='Model' then sb=ms;
  if source='Error' then sw=ms;
  if last then do;
    ICC=round((sb-sw)/(sb+sw), 0.01);
    output;
  end;
run;

```

The analyses will be performed using the FAS.

The tables and figures that will be displayed are detailed in Section 6.1.2.1.3.

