### 5.5.3.3 *Inter- Off-Site Reader Variability*

Inter-reading variability will be evaluated on the whole set of study subjects, since each case was read by 3 different readers.

The same methodology as the one presented above for intra-off-site variability will be applied. One scatter plot for each of the 3 comparisons will be presented. The factor “reader” will be used instead of the factor “reading” in the model.

The tables and figures that will be displayed are detailed in Section 6.1.2.1.3.

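### SAP 5.5.3.2–5.5.3.3: the Bland-Altman limits are built from the averages instead of the differences, and the coded ICC rises when readings disagree systematically

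*SAP*

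**What the plan says.** Section 5.5.3.2 opens with "Intra-central reader variability will be studied by a Bland-Altman graph". The average of the first and second readings is on the X axis and the second reading minus the first is on the Y axis. Horizontal lines are drawn at 0 and at Mean ± 1.96 SD, "where Mean and SD are the mean and the SD of the averages of" the two readings.

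For the ICC, the text says "It will be based on a one-way random effect model without observed effect". The estimator is (MSα − MSε)/(MSα + MSε), and the two terms "are the mean sums of squares from the one-way ANalysis Of VAriance (ANOVA) model for between and within subjects, respectively".

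The SAS code does something else. It fits "model BV = patno reading", captures the overall table with "ods output OverallANOVA =icc0", and assigns the between-subject term with "if source='Model' then sb=ms". The Error mean square becomes the within-subject term, and the code returns (sb − sw)/(sb + sw).

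Section 5.5.3.3 covers agreement between the three off-site readers: "The same methodology as the one presented above for intra-off-site variability will be applied". Reader replaces reading in the model, and there is one scatter plot for each of the three comparisons.

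**The concern.** There are three separate faults.

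1. **Limits of agreement.** Lines drawn on a difference axis must come from the differences. Lines from the averages are centred on mean CNR, and their width is mostly between-subject variation.
2. **ICC code against ICC text.** The overall Model mean square pools subject and reading. A constant shift between readings therefore inflates the between-subject term and is removed from the error term, so worse systematic disagreement gives a better ICC. The text's one-way estimator behaves correctly, so text and code contradict each other.
3. **Number of readings.** The estimator is right for two readings. With three readers in one model the denominator should be MSα + 2MSε.

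Protocol 9.4.8 promises intra- and inter-reader variability in the final analysis. The primary test is run reader by reader, and protocol 12.3 calls a dose effective when at least two of the three readers meet the alternative hypothesis. Readers of the report will use these agreement statistics to judge how far the per-reader results can be trusted.

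**Working it through.** The SAP states no agreement result, so there is no figure to reproduce. The direction of each error follows from algebra. The sizes below are illustrations.

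**Inputs.** Between-subject SD σb = 3.01, borrowed from SAP 3.3 (σb² = 9.0601). The documents give no mean CNR. Solving the sample-size statement (30% increase, 50 per group, 90% power, t-test) for the control mean gives 4.7 (paired, one-sided 0.025) to 7.7 (two-sample, one-sided 0.025/4), so I use 4.7, 5.5 and 7.7. Repeat-read SDs and shifts are assumed. The intra-reader sample is 10% of 240 = 24 subjects.

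**Bland-Altman, read SD σe = 0.75, no shift**

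- SD of averages = √(9.0601 + 0.75²/2) = 3.056; 1.96 × 3.056 = 5.99.
- SD of differences = 0.75 × √2 = 1.061; 1.96 × 1.061 = 2.08.
- At mean 5.5 the planned lines are 5.5 ± 5.99 = −0.49 to 11.49. Correct limits are −2.08 to 2.08.
- Share of differences outside the planned lines: Φ(−0.49/1.061) = 32%. At mean 4.7 (lower line −1.29) it is 11%; at mean 7.7 (lower line 1.71) it is 95%. Proper limits leave 5% outside.

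**ICC, two readings, n = 24, σe = 2, shift d**

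- Expected subject mean square MSB = 2 × 9.0601 + 4 = 22.12.
- Expected SS for reading = 4 + 24d²/2.
- Code: sb = (23 × 22.12 + SS_reading)/24; sw = 4, whatever d is.
- Text: MSW = (23 × 4 + SS_reading)/24; ICC = (MSB − MSW)/(MSB + MSW).

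| d | SS_reading | sb (code) | MSW (text) | ICC, code | ICC, text |
|---|---|---|---|---|---|
| 0 | 4 | 21.37 | 4.00 | 0.68 | 0.69 |
| 1 | 16 | 21.87 | 4.50 | 0.69 | 0.66 |
| 1.5 | 31 | 22.49 | 5.13 | 0.70 | 0.62 |
| 3 | 112 | 25.87 | 8.50 | 0.73 | 0.44 |
| 6 | 436 | 39.37 | 22.00 | 0.82 | 0.00 |

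These use expected mean squares; averages over simulated data sets are close (0.72 against 0.42 at d = 3, 0.81 against about 0 at d = 6). Because d² enters sb and never sw, the coded ICC must increase with |d|. In 500 further simulated data sets it rose at every step of increasing shift.

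**ICC, three readers in one model, n = 200, σe = σb = 3.01 (true ICC 0.50)**

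- No shift: MSB = 4σe² and MSW = σe². The SAP formula gives (4 − 1)/(4 + 1) = 0.60; the three-reader formula gives (4 − 1)/(4 + 2) = 0.50.
- Reader shifts 0, 3 and 6: SS_reader = 2 × 9.0601 + 200 × 18 = 3618.1. Code: sb = (199 × 36.24 + 3618.1)/201 = 53.88 and sw = 9.06, so ICC = 44.82/62.94 = 0.71. One-way with k = 3: MSW = (398 × 9.06 + 3618.1)/400 = 18.06, so ICC = 18.18/72.36 = 0.25.

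**The case against.** The wording on averages and the mismatch between code and text cannot be defended. The case on the other side concerns scope and size.

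- **Pairwise ICC.** Section 5.5.3.3 specifies one plot per reader comparison. If the ICC is also pairwise, two readings apply and the formula is right. This stands: the three-reader figures hold only if all readers enter one model, which the SAP does not settle. Pairwise use does not cure the code. With n = 200, true ICC 0.50 and a shift of 6, it gives 0.67 against about 0.
- **Small shifts.** One reader re-reading the same images may shift little. At shifts up to 1 unit the code and the text differ by about 0.03 or less. This also stands: the ICC fault matters mainly between readers.
- **Bias visible elsewhere.** The plot shows every difference against a zero line, 5.5.2.3 gives CNR by reader, and 5.5.2.2 fits reader and its interaction with treatment. A large shift would probably be noticed, but the reported ICC would still be wrong.
- **Limited consequence.** The SAP classes these as additional analyses. They set no threshold and feed neither the primary test nor dose selection. Agreed.
- **Unseen shells.** Table and figure shells are in attachments outside the public SAP. They might define the limits differently, but the SAP text would still need correcting.

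**Conclusion.** Wrong as written, and it should be corrected. The Bland-Altman lines are not limits of agreement for any data. In the illustration they leave 11% to 95% of differences outside, depending on mean CNR. The coded ICC contradicts the SAP's own definition and increases with systematic disagreement: 0.73 against 0.44 at a shift of 3 units. If three readers enter one model, a true 0.50 is reported as about 0.60 even with no shift.

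The direction of these errors does not depend on assumptions. Their size rests on the assumed between-subject SD, mean CNR, read SDs and shifts, none of which the documents give for reader agreement. The primary comparison, its alpha and the sample size are untouched.

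**What to change.** - **Bland-Altman:** draw lines at 0, at the mean of the differences, and at that mean ± 1.96 SD of the differences.
- **ICC model:** fit subject alone (model BV = patno), so that Model and Error are the between- and within-subject mean squares the text defines.
- **ICC formula:** use (MSB − MSW)/(MSB + (k − 1)MSW), with k = 2 for repeat readings. For readers, state either k = 3 in one model or k = 2 for each pair.
- **Data set:** define BV and state that one value per subject per reading enters each model, for example separately by contrast agent. Each subject has two MRIs. If both enter under one subject number, the difference between agents falls into the within-subject error and k is no longer 2.

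The cost is a few lines of SAP text and code, with no new data. The reported ICC will fall wherever readings are systematically shifted, and will barely change for two readings without a shift.

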### 5.5.3.3 *Inter- Off-Site Reader Variability*

Inter-reading variability will be evaluated on the whole set of study subjects, since each case was read by 3 different readers.

The same methodology as the one presented above for intra-off-site variability will be applied. One scatter plot for each of the 3 comparisons will be presented. The factor “reader” will be used instead of the factor “reading” in the model.

The tables and figures that will be displayed are detailed in Section 6.1.2.1.3.

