In addition of these subjects, two hundred and forty (240) subjects will be enrolled in a second subset (subset 2, see [Figure 1](#)). These subjects will be used for dose-finding part of the study in which the safety and diagnostic efficacy of P03277 will be evaluated in CNS MRI at doses of 0.025, 0.05, 0.1 and 0.2 mmol/kg (doses driven by efficacy in a safety acceptable range) with a 1:1:1:1: ratio versus MultiHance® (0.1 mmol/kg BW).

Subjects from both subsets will receive one of the doses of P03277 and one dose of MultiHance® by single IV injection at a rate of 2 mL/second followed by 0.9% saline flush in randomized order in two successive treatment periods separated by a wash out period of 2 days minimum up to 14 days.

During the course of the study, 2 MRIs will be obtained from each subject: one unenhanced and P03277-enhanced MRI; and one unenhanced and MultiHance®-enhanced MRI. MRI evaluations will be performed by on-site investigators and 3 independent off-site blinded readers.

To determine the exact matching of lesions throughout the different imaging sequences and MRI examination (P03277 and MultiHance®), an independent radiologist (lesion tracker) will perform 'lesion tracking' (except for the global matched pairs evaluation) based on the available CNS (brain/spinal cord) diagrams 

 CONFIDENTIAL	Protocol No. GDX-44-004 Version No. 2.0 (Protocol including amendment n°1) Date: 11 July , 2016	 Page 24 / 84
----------------------------------------------------------------------------------------------------------	----------------------------------------------------------------------------------------------------------	-----------------------------------------------------------------------------------------------------

The safety of subjects will be assessed using vital signs, 12-lead ECGs, injection site tolerance, clinical laboratory parameters (blood and urine) and by monitoring of adverse events (AEs). Safety assessments will be conducted over 1 day follow-up period after each MRI visit.

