#### 9.4.8 *Inter & Intra-Reader Variability Assessment*

The assessments of inter- and intra-reader variability will be done in the final analysis.

- **Inter-reader variability** will be evaluated on the whole set of study subjects, since each case will be read by 3 different readers.
- **Intra-reader variability:** individual readers will perform repeat image evaluations of 10% of cases randomly determined. The cases used for intra-reader variability assessment will be re-introduced randomly and re-read during the course of the reading. To minimize recall bias, intra-reader variability will be assessed approximately after the first 30 cases are reviewed and no sooner than two weeks from the original reviews of these subjects. Results of the original reviews for these cases will not be available to the reader. Only the first evaluation of a given image set will be included in the efficacy analysis.

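### The inter-reader ICC in SAP 5.5.3.3 carries a two-measurement formula over to three readers, and the visible text does not separate a subject's two exams

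*SAP*

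**What the plan says.** SAP 5.5.3.2 (intra-reader) introduces the ICC with "It will be based on a one-way random effect model without observed effect". The model puts three subscripts on each reading but has only a subject effect and an error; the second and third subscripts are not defined. The estimator is (MSa − MSe)/(MSa + MSe), coded as "ICC=round((sb-sw)/(sb+sw), 0.01". The PROC GLM step fits "model BV = patno reading" and takes its between-subject mean square from the overall model line: "if source='Model' then sb=ms". The only stated level of repetition is the reader: "SAS® procedure used for the analyses of this secondary efficacy criterion will be the following for each off-site reader". The code has no agent, exam, period or dose term and no BY statement. The input dataset `intra` and the response `BV` are not described.

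SAP 5.5.3.3 (inter-reader) says "The same methodology as the one presented above for intra-off-site variability will be applied". The only stated change to the model is that the factor for reader replaces the factor for reading. Three comparisons are mentioned, but only for the scatter plots.

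Two facts from the protocol matter here. Section 9.4.8 says "each case will be read by 3 different readers". Section 3.1 says "During the course of the study, 2 MRIs will be obtained from each subject", one with each agent.

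**The concern.** Two features of the stated method fit the data poorly.

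- **Formula.** The denominator MSa + MSe is the special case of MSa + (k − 1)MSe at k = 2, where k is the number of values per unit. Two readings by one reader satisfy this. Three readers do not.
- **Unit.** CNR exists per exam, and each subject has two exams with different agents. With `patno` as the only unit, nothing in the visible model keeps those exams apart. If both are in the dataset, the difference between agents falls into the error term and is counted as reader disagreement.

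At stake is whether the reported ICC can be read as reader agreement. CNR is measured and tested reader by reader, so readers of the report will look to this figure to judge how reproducible those measurements are.

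**Working it through.** The documents give no ICC value, target or precision, so there is no figure to reproduce. The check is of what the stated estimator targets.

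**1. Number of values per unit.** In a balanced one-way layout with k values per subject and true ICC ρ, E[MSa] = σe² + kσa² and E[MSe] = σe². The SAP ratio therefore targets kρ/(kρ + 2(1 − ρ)).

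- k = 2 (two readings, one exam): the ratio equals ρ, which is correct.
- k = 3 (three readers, one exam): the ratio is 3ρ/(2 + ρ). For ρ = 0.40, 1.2/2.4 = 0.50. For ρ = 0.60, 1.8/2.6 = 0.69. For ρ = 0.80, 2.4/2.8 = 0.86. It is too high for every ρ between 0 and 1.
- Both exams stacked, no difference of any kind between them: k = 4 for re-reads and k = 6 for three readers. For ρ = 0.50 the ratio is 2.0/3.0 = 0.67 and 3.0/4.0 = 0.75.

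**2. Both exams stacked, with an agent difference d.** Let σs² be variance shared by a subject's two exams, σx² exam-specific variance and σe² reader error. For three readers:

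- MSa = σe² + 3σx² + 6σs²
- MSe = σe² + 0.6σx² + 0.3d²

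Assumptions: the total SD of a reading is 3.01 (the SAP 3.3 value; variance 9.060) and true same-exam ICC is 0.80, so σe² = 1.812 and σs² + σx² = 7.248. The control mean CNR is not given, so d was backed out from 50 subjects, SD 3.01 and 90% power: 1.38 (paired, one-sided 0.025), 1.95 (two-sample, 0.025) and 2.27 (two-sample, 0.025/4). The values 0 and 4 were added as extremes. One common d is used for all subjects.

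- All true variance shared, d = 2.27: MSa = 1.812 + 43.488 = 45.30; MSe = 1.812 + 1.546 = 3.36; ratio 41.94/48.66 = 0.86.
- 60% shared (σs² = 4.349, σx² = 2.899), d = 2.27: MSa = 1.812 + 8.697 + 26.094 = 36.60; MSe = 1.812 + 1.739 + 1.546 = 5.10; ratio 31.50/41.70 = 0.76.

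Simulation of the SAP code (400 runs per cell, true ICC 0.80):

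| Layout | d = 0 | 1.38 | 1.95 | 2.27 | 4 |
|---|---|---|---|---|---|
| 3 readers, n = 200, fully shared | 0.922 | 0.898 | 0.877 | 0.860 | 0.739 |
| 3 readers, n = 200, 60% shared | 0.818 | 0.794 | 0.768 | 0.752 | 0.625 |
| 2 readings, n = 24, fully shared | 0.874 | 0.830 | 0.800 | 0.771 | 0.589 |
| 2 readings, n = 24, 60% shared | 0.704 | 0.677 | 0.636 | 0.600 | 0.433 |

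Reader error is the same in every cell. The n of 24 is 10% of 240.

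**3. Mean square taken by the code.** The text describes a one-way model, but the code fits subject plus reading and uses the overall Model mean square, so a systematic shift between readings enters the numerator. With one exam, two readings, n = 24 and true ICC 0.50, a shift of 2 units moves the coded value from 0.46 up to 0.53, while the one-way ICC falls from 0.47 to 0.33.

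**4. Corrected estimator.** Each exam was analysed on its own, with a one-way model and (MSa − MSe)/(MSa + (k − 1)MSe). For true 0.80 with both exams collected, this returned 0.797 to 0.801 with three readers and 0.783 to 0.790 with two readings, at every d. The small shortfall with two readings is small-sample bias.

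**The case against.** The best defence is that the programmer may do the right thing. Bland-Altman plots are pairwise by construction. If the ICC follows the same three reader pairs, k = 2 and the formula is correct. The dataset may also be built per agent: SAP 3.1 promises results by group, and Protocol 9.4.8 speaks of cases and image sets rather than of subjects with both exams combined. The list of tables in SAP section 6 is blank in the public copy and the table shells are in an attachment not included, so a detail kept there cannot be called missing from the plan.

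Much of this stands. A reader might infer that the plan pools the two exams as repeat readings. The documents do not establish that; they show only that the visible model and code do not separate them. A reader might also infer that pooling would always lower the ICC. It would not: with fully shared variance and three readers, a true 0.80 comes out at 0.86 to 0.92 for differences of 2.27 down to 0.

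The defence does not clear the text, however. The pairwise wording is attached to the plots, not to the ICC. Separating agents alone leaves the k = 3 error, and pairing readers alone leaves the exams together. The inter-reader figure is right only if both unstated choices are made.

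**Conclusion.** On the literal text the inter-reader ICC is wrong, and in a known direction: with three readers and one exam per subject it overstates agreement, by 0.10, 0.09 and 0.06 at true values of 0.40, 0.60 and 0.80. This needs no assumption beyond a three-reader ICC in a balanced layout.

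The second part is conditional. If both exams enter under one subject, there are 4 or 6 values per unit and the figure depends on the agent difference. Its size and direction rest on the assumed sharing of variance between exams and on the assumed differences, so the table shows sensitivity and is not a forecast.

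The consequence is limited. The ICC is listed among additional analyses, has no threshold, and feeds neither the CNR test nor dose selection. A reader might link it to the rule in Protocol 12.3 that at least two of three readers must meet the alternative hypothesis, but neither document makes that rule depend on the ICC. The point is still worth correcting before analysis, because the SAP states a specific estimator that gives a wrong number when followed as written.

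**What to change.** In SAP 5.5.3.2 and 5.5.3.3:

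- State that the exam is the unit. Compute the ICC separately for P03277 and MultiHance exams, or use `patno*trt` as the unit with agent in the model.
- Take the between-unit mean square for that unit, from a model that matches the one-way text, instead of the overall Model mean square.
- Use (MSa − MSe)/(MSa + (k − 1)MSe) with k = 2 for intra-reader and k = 3 for inter-reader. Alternatively, state that three pairwise ICCs will be given, each with k = 2.
- Define the dataset, the response and the subscripts.

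The cost is SAP wording and a few lines of code, with no new data. The drawback is that the reported inter-reader figure may be less favourable.

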#### 5.5.4. Analysis of secondary criteria

Depending on the way they were collected, the criteria will be displayed for the off-site readings and/or the on-site reading. Descriptions will be systematically done by reader. Analyses of secondary criteria will be described using the FAS only, except the first three criteria for which the PPS will be considered also (for matching lesions only).

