### 7.2.1 *Technical adequacy of images (on-site and off-site reads)*

Combined images sets (1a, 2) and (1b, 3) will be evaluated as adequate or not. Images are considered technically inadequate if artifacts completely compromise image interpretability. The reasons will be recorded:

- 1 = Artifacts due to subject
- 2 = Artifacts due to machine
- 3 = Artifacts due to contrast agent
- 4 = Injection technical failure
- 5 = Other, specify

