### 12.1 Subjects Included in the Analysis

There will be four subject sets defined for this study: the Extended Set (ES), the Safety Set (SS), the Full Analysis Set (FAS) and the Per-Protocol Set (PPS).

The Extended Set will include all subjects with available data. This set will be used for subject disposition summaries and individual listings.

The Safety Set will include all subjects, receiving at least one injection of contrast agent, regardless of the quantity. Subjects of subset 1 will be included in this set. This set will be used for evaluation of safety.

The Full Analysis Set will include all subjects, except subjects from subset 1, who have valid assessments of the primary criterion. This set will be used for description of demographic data, baseline characteristics data, medical history, concomitant treatment and evaluation of efficacy.

The Per Protocol Set will be a subset of the FAS and will include all subjects who have no major protocol deviations throughout their whole study period. This set will be used for the evaluation of the primary efficacy criterion.

If the PP set differs from the FAS by more than 15%, description of demographic data, medical history, concomitant treatment and evaluation of efficacy will be repeated for this set.

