#### Analyses of the secondary criteria

All analyses of the secondary criteria (based on combined unenhanced/enhanced contrast images) will be done using the FAS except otherwise specified.

- **Technical adequacy of images**
  - The adequacy of images will be assessed by off-site readers and on-site radiologists as adequate, yes or no and reason for inadequacy will be recorded using a 5-items list. Adequacy of images will be tabulated for each dose of P03277 by treatment groups; off-site and on-site reader's outcomes will be separately analyzed.

Guerbet    CONFIDENTIAL	Protocol No. GDX-44-004 Version No. 2.0 (Protocol including amendment n°1) Date: 11 July , 2016	 Page 63 / 84
---------------------------------------------------------------------------------------------------------------------------	----------------------------------------------------------------------------------------------------------	-----------------------------------------------------------------------------------------------------

- **Lesion visualization variables**

- Off-site blinded readers and on-site radiologists will grade the lesion visualization of the three largest representative lesions, using 3 variables (lesion border delineation, internal morphology and degree of contrast enhancement) assessed on a 4-point scale ranging from 1 to 4.

For each variable, one subject score will be computed in adding up all lesion scores within subject by treatment groups.

Subject score will be tabulated for each dose of P03277 by treatment groups; each off-site and on-site reader's outcomes will be separately analyzed.

- Dose/response evaluation as per primary endpoint will be performed also for the subject score of each lesion visualization variable by each off-site reader.

- **Lesion detection capacity**

- The number of lesions by subject will be assessed by off-site readers and on-site radiologists for each dose of P03277 by treatment groups. Number of lesions will be tabulated for each dose of P03277 by treatment groups; off-site and on-site reader's outcomes will be separately analyzed.

- The size of the three largest representative lesions by subject will be assessed by off-site readers and on-site radiologists for each dose of P03277 by treatment groups. Size of lesion will be summarized for each dose of P03277 by treatment groups; off-site and on-site reader's outcomes will be separately analyzed.

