## 5.2. Data Sets Analysed and protocol deviations

### 5.2.1. Data Sets Analysed

There will be four subject sets defined for this study: the Extended Set, the Safety Set, the FAS and the PPS.

The Extended Set will include all subjects having signed the Informed Consent Form (ICF). This set will be used for subject disposition summaries, overall summary of AEs and individual listings.

The Safety Set will include all subjects, receiving at least one injection of contrast agent, regardless of the quantity. Subjects of subset 1 will be included in this set. This set will be used for description of demographic data, medical history, previous treatments and evaluation of safety. Analyses using the Safety Set will be based on the contrast agent actually received.

The FAS will include all subjects from subset 2 who have a CNR from both enhanced and unenhanced measurements derivable from one MRI by at least one off-site blinded reader. This set will be used for description of demographic data, baseline characteristics data, medical history, previous treatments and evaluation of efficacy. Analyses using the FAS will be based on the contrast agent allocated by the randomization whatever the contrast agent actually received, following the Intention To Treat (ITT) principle.

The PPS will be a subset of the FAS and will include all subjects who have no major protocol deviations (see below) throughout their whole study period. This set will be used for the evaluation of the primary efficacy criterion and main secondary criteria.

CONFIDENTIAL	
FORM
 
STATISTICAL ANALYSIS PLAN N° GDX-44-004
 
VERSION 1.0      DATED: 09JAN2018
	[REDACTED]
--------------	---	------------

Page 19 / 60

Analysis data sets will be presented on the Extended Set: subjects included in the Safety Set by contrast agent actually received and globally and included in the FAS and in the PPS by contrast agent allocated by the randomization and globally.

The tables and the listing that will be displayed are detailed in Sections 6.1.1.3 and 6.2.3.

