#### 5.5.4.4 *Technical Adequacy of Images*

The adequacy of images was assessed by off-site readers and on-site radiologists as adequate or not and reason for inadequacy (with specification in case of other reason) recorded using a 5-items list.

Descriptive statistics for these secondary efficacy criteria will be presented by contrast agent group.

The tables and listings that will be displayed are detailed in Sections 6.1.2.2.4 and 6.2.6.2 respectively.

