For each dose of P03277 SAS® procedure used for the analyses of this secondary efficacy criterion will be the following for each off-site reader and on-site reading:

```

proc glimmix data = XXX;
  class subject trt period;
  model eval = trt period / dist = negbin link = id;
  random _residual_ / subject = subject type = cs;
  lsmeans trt / pdiff = controlu('MultiHance') tdiff cl alpha = 0.025;
  lsmeans trt;
  estimate "P03277 - MultiHance" trt 1 -1 /cl;
run;

```

The number of lesions detected on off-site readings will be listed only.

The *absence of contrast enhancement* is defined **at lesion level** by a degree of contrast enhancement equal to 1 = no: no enhancement. The absence of contrast enhancement will be analyzed **at subject level** only by considering its absence as soon as it is absent for all lesions. It will be presented by descriptive statistics.

The tables and listings that will be displayed are detailed in Sections 0 and 6.2.6.2 respectively.

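### Technical adequacy is tabulated on a set that requires a derivable CNR, so subjects with only inadequate exams are not counted and adequacy can be overstated, by an amount the documents do not fix

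*SAP*

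**What the plan says.** **Analysis set.** SAP 5.5.4 says "Analyses of secondary criteria will be described using the FAS only" and adds the PPS only for the first three criteria listed there (CSF-based CNR, lesion-to-brain ratio and contrast enhancement percentage). Protocol 12.3 agrees: "All analyses of the secondary criteria (based on combined unenhanced/enhanced contrast images) will be done using the FAS except otherwise specified". For technical adequacy, SAP 5.5.4.4 names no other set and says only "Descriptive statistics for these secondary efficacy criteria will be presented by contrast agent group".

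**Who is in the FAS.** SAP 5.2.1 includes subset 2 subjects "who have a CNR from both enhanced and unenhanced measurements derivable from one MRI by at least one off-site blinded reader". The condition in protocol 12.1 is of the same kind: "The Full Analysis Set will include all subjects, except subjects from subset 1, who have valid assessments of the primary criterion".

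**What counts as inadequate.** Protocol 7.2.1: "Images are considered technically inadequate if artifacts completely compromise image interpretability". The recorded reasons include artifacts caused by the contrast agent and technical failure of the injection. Off-site readers and investigators both make this assessment.

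**Absence of enhancement.** SAP 5.5.4.5 analyses this at subject level, "only by considering its absence as soon as it is absent for all lesions". SAP 2.2.1 averages CNR over up to three enhanced lesions, and the protocol synopsis places the lesion ROIs in enhancing areas.

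**The concern.** The adequacy table is meant to count exams that could not be interpreted, and an exam of that kind is not expected to yield a CNR. If every exam a subject had was of that kind for every off-site reader, the subject is outside the FAS and the failed exams appear in neither numerator nor denominator. A subject who stopped after one inadequate exam is lost in the same way. The investigator's own adequacy grade goes too, because FAS membership depends on the off-site readers.

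What is at stake is the absolute adequacy rate for each agent, a stated secondary objective. Some of the recorded reasons for inadequacy relate to the product or its injection, so the lost exams could be informative ones.

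A separate issue affects the absence-of-enhancement summary. If CNR exists only for enhanced lesions, a subject with no enhancement at any exam also has no CNR and drops out of the table that would count that subject.

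**Working it through.** **1. The plan's own denominator.** Protocol section 8: 4 dose groups × (50 + 10) = 240 randomised in subset 2, or 60 per group. This reproduces. No inadequacy or non-enhancement rate is given, so every rate below is an assumption.

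**2. Adequacy with two exams per subject.** Let a be the proportion of subjects inadequate at both exams for all off-site readers, and b the proportion inadequate at exactly one.

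- All exams performed: adequacy = 1 − (2a + b)/2.
- FAS, which drops the a group: adequacy = 1 − b/[2(1 − a)].

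With 240 subjects and 480 exams:

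| Assumption | All exams | FAS | Difference (points) |
|---|---|---|---|
| a = 0, any b | 1 − b/2 | 1 − b/2 | 0 |
| Independent failures, 3% per exam: a = 0.03² = 0.0009, b = 2 × 0.03 × 0.97 = 0.0582 | 97.0% | 1 − 0.0582/1.9982 = 97.1% | 0.1 |
| a = 1%, b = 1% | 1 − 7.2/480 = 98.5% | 1 − 2.4/475.2 = 99.5% | 1.0 |
| a = 2%, b = 2% | 1 − 14.4/480 = 97.0% | 1 − 4.8/470.4 = 99.0% | 2.0 |
| a = 5%, b = 2% | 1 − 28.8/480 = 94.0% | 1 − 4.8/456 = 98.9% | 4.9 |

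The last three rows build in strong within-subject correlation. The chance of failing the second exam given failure at the first is a/(a + b/2): 0.01/0.015 = 67%, 0.02/0.03 = 67% and 0.05/0.06 = 83%. Under independence it is 3%, and the expected number failing both is 240 × 0.0009 = 0.2 subjects.

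**3. Subjects with one exam.** Suppose all 40 subjects in the dropout allowance (4 × 10) had exactly one exam, with independent failures at 3%. There are 400 + 40 = 440 exams, of which 13.2 are inadequate. The FAS loses 40 × 0.03 = 1.2 exams from single-exam subjects and 200 × 0.0009 × 2 = 0.36 from the others. Its adequacy is 1 − (13.2 − 1.56)/(440 − 1.56) = 97.3% against 97.0%, a difference of 0.3 point.

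**4. Per dose group of 60, one agent.** If k subjects have only inadequate exams and no other exam is inadequate, the FAS shows 100%. All-imaged adequacy is 59/60 = 98.3% for k = 1 and 57/60 = 95.0% for k = 3.

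**5. Non-enhancing subjects and adequacy.** Take k = 0, two inadequate exams kept in the FAS, and three readable but non-enhancing subjects excluded. The FAS gives 55/57 = 96.5% and all imaged gives 58/60 = 96.7%. Adequacy falls by 0.2 point.

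**6. Non-enhancing subjects and absence of enhancement.** Take 60 subjects, three retained subjects with absence at this agent's exam, and m subjects with no enhancement at any exam, excluded from the FAS. Absence is 3/(60 − m) on the FAS against (3 + m)/60 on all imaged: 5.1% against 6.7% (m = 1), 5.3% against 10.0% (m = 3) and 5.6% against 15.0% (m = 6).

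**The case against.** **The FAS rule is lenient.** One usable MRI for one of three readers keeps a subject in, and any inadequate other exam is still counted. Complete loss needs failure for all off-site readers at every exam done. Site qualification on the first subject's images (protocol 9.4.2) and the core laboratory's quality checks (protocol 9.4.4) should make that uncommon. This stands, and it is why zero or a fraction of a point is a realistic size. Single-exam subjects remain exposed.

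**The failures are traceable.** Listings cover all subjects (SAP section 7), analysis-set membership is tabulated on the Extended Set (SAP 5.2.1), and so are major deviations (SAP 5.2.2). A reader might infer that failures are hidden altogether, and the documents do not support that. But a listing does not correct the tabulated rate.

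**The SAP follows the protocol, and the adequacy table is descriptive.** Both are true. Yet the SAP widens a set elsewhere when the purpose calls for it: SAP 5.6.2.1 uses the Extended Set so that adverse events in uninjected subjects are not missed.

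**Exclusion of non-enhancing subjects is not explicit.** The CNR formula can be computed for any lesion ROI, and the SAP itself computes it on unenhanced images. No rule says that a lesion graded as having no enhancement has no derivable CNR. Inclusion criterion 2 also requires an expected enhancing lesion, so absence at every exam should be uncommon. This stands, so the second part is worded as probable.

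**The per-table list cannot be checked.** The content of SAP section 6 is redacted and the table shells are separate attachments, so a table-level population may exist there. No visible text names one.

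**Conclusion.** The concern holds in a limited form. The visible text makes inclusion in the adequacy table conditional on at least one exam having yielded a CNR. Any subject with only inadequate exams is left out, which overstates adequacy in both the off-site and on-site tables. The size cannot be fixed from the documents. It is zero with no such subject, about 0.1 point under independence at 97% per-exam adequacy, and about 2 points if 2% fail at both exams and 2% at one. Larger values need the strong within-subject correlation shown in the working, for which the documents offer no evidence.

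Two stronger readings are tempting and not supported. The first is that losing non-enhancing subjects also inflates adequacy. A readable exam without enhancement is adequate, so dropping it lowers the rate slightly. Its probable effect is to understate absence of enhancement. The second is that the comparison of P03277 with MultiHance® is distorted to the same degree. A subject inadequate at both exams is removed from both agents' columns, so the contrast is affected less than the absolute rates, single-exam subjects excepted.

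This is a minor point about descriptive tables. The primary test and sample size are untouched.

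**What to change.** Tabulate technical adequacy and absence of enhancement, by reader and contrast agent, on all subset 2 subjects who were injected and had at least one study MRI, with exams performed as the denominator. In the absence-of-enhancement table, show inadequate exams as a separate not-assessable row. The FAS version may be kept alongside. Keep the FAS for the CNR-based criteria.

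State in SAP 5.2.1 whether a lesion graded as having no enhancement yields a CNR, and hence whether a subject with only such lesions enters the FAS.

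Record the change in SAP section 4 as a departure from protocol 12.3. The cost is that departure from the protocol-named set for two descriptive summaries, plus some reprogramming. The data are already collected.
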